1.0 Introduction

This Statistical Analysis Plan (SAP) describes the statistical analyses for Atogepant (AGN-241689) Study M22-056 A Phase 2/3, Multicenter, Randomized, Double-Blind, Placebo Controlled, Parallel-Group Study with An Active Treatment Extension to Evaluate the Efficacy, Safety, and Tolerability of Oral Atogepant for the Prevention of Migraine in Japanese Subjects with Episodic Migraine.

Study M22-056 examines the efficacy and safety of Atogepant (AGN-241689) in Japanese subjects with episodic migraine.

The analyses of pharmacokinetic and pharmacodynamic endpoints and exploratory biomarker endpoints will not be covered in this SAP.

The SAP will not be updated in case of administrative changes or amendments to the protocol unless the changes impact the analysis.

Unless noted otherwise, all analyses will be performed using SAS Version 9.4 (SAS Institute Inc., Cary, NC 27513) or later.

2.0 Study Objectives and Design

2.1 Study Objectives

The primary objective of the trial is to evaluate the safety, efficacy and tolerability of atogepant 10 mg, atogepant 30 mg, and atogepant 60 mg once daily for the prevention of migraine in Japanese subjects with episodic migraine, and to prospectively test for superiority of atogepant 10 mg, atogepant 30 mg, or atogepant 60 mg QD versus placebo for the prevention of migraine in Japanese subjects with episodic migraine.

The estimand corresponding to the primary efficacy objective is defined as follows:

- The difference in the mean change from baseline in mean monthly migraine days across the 12-week double-blind treatment period between each atogepant group and placebo in adult patients with episodic migraine who require

preventive treatment of migraine. Data collected during the double-blind treatment period are included in the analyses. Missing data for subjects who discontinued the study treatment due to any reason are assumed MAR, i.e., subjects with treatment discontinuation behave like other subjects who did not discontinue the study treatment. Use of acute migraine medication as rescue medications is considered in the definition of migraine/headache day (composite strategy).

The secondary objective is to demonstrate improvement in efficacy for treatment with atogepant when each of atogepant doses is compared to placebo with respect to the secondary endpoints.

The estimands corresponding to the secondary efficacy endpoints are:

- The difference in the mean change from baseline in mean monthly headache days across the 12-week treatment period between each atogepant group and placebo in adult patients with episodic migraine who require preventive treatment of migraine. Data after the discontinuation from double-blind treatment period are assumed MAR. Use of acute migraine medication as rescue medications is considered in the definition of migraine/headache day (composite strategy).
- The difference in the mean change from baseline in mean monthly acute medication use days across the 12-week treatment period between each atogepant group and placebo in adult patients with episodic migraine who require preventive treatment of migraine. Data after the discontinuation from double-blind treatment period are assumed MAR.
- The odds ratio in subjects achieving at least 50% reduction from baseline in 3-month average of monthly migraine days between each atogepant group and placebo in adult patients with episodic migraine who require preventive treatment of migraine. Use of acute migraine medication as rescue medications is considered in the definition of migraine/headache day (composite strategy).
- The difference in the mean change from baseline in MSQ v2.1 Role Function Restrictive domain score at Week 12 between each atogepant group and placebo in adult patients with episodic migraine who require preventive

treatment of migraine. Data after the discontinuation from double-blind treatment period are assumed MAR.

- The difference in the mean change from baseline in mean monthly Performance of Daily Activities domain score of the AIM-D across the 12-week treatment period between each atogepant group and placebo in adult patients with episodic migraine who require preventive treatment of migraine. Data after the discontinuation from double-blind treatment period are assumed MAR.
- The difference in the mean change from baseline in mean monthly Physical Impairment domain score of the AIM -D across the 12-week treatment period between each atogepant group and placebo in adult patients with episodic migraine who require preventive treatment of migraine. Data after the discontinuation from double-blind treatment period are assumed MAR.

2.2 Study Design Overview

This is a multicenter, randomized, double-blind, placebo controlled, parallel group Phase 2/3 study that evaluates the safety, efficacy, and tolerability of atogepant in Japanese subjects. The study consists of a 4-week screening and baseline period, a 12-week double-blind treatment period, a 12-week blinded active treatment extension period, and a follow-up Period 30 days after the last dose of study drug, for a total duration of approximately 32 weeks.

Subject participation will begin with a 4-week screening/baseline period. Subjects who complete the 4-week screening/baseline period and meet all entry criteria will be randomized to the double-blind treatment period of the study at Visit 2 (Randomization Visit). The double-blind treatment period will last 12 weeks, and all completers move to the 12-week active treatment extension period with a subsequent follow-up Period 30 days after the last dose of study drug. For details, please see [Figure 1](#), Study Schematic.

[figure not shown]
All completers of the double-blind treatment period may continue into the active treatment extension period (dose will be blinded). Subjects who are randomized to atogepant treatment groups in the double-blind treatment period will continue to be

assigned to the same dose treatment group in the active treatment extension period. Subjects in the placebo group in the double-blind treatment period will be re-randomized to either the atogepant 10 mg, atogepant 30 mg, or atogepant 60 mg treatment arm (dose blinded) in a 1:1:1 ratio in the active treatment extension period.

An eDiary will be used to record the daily total duration of headache, headache characteristics, associated symptoms, the worst pain severity, and acute medication use both in the screening/baseline period and double-blind treatment period until Visit 5.

The schematic of the study is shown in [Figure 1](#).

Figure 1. Study Schematic

2.3 Treatment Assignment and Blinding

On Study Day 1 of the Double-Blind Treatment Period, approximately 520 subjects will be randomized to one of the following 4 arms in a 1:1:1:1 ratio:

- Placebo (n = 130)
- Atogepant 10 mg (n = 130)
- Atogepant 30 mg (n = 130)
- Atogepant 60 mg (n = 130)

The study will be enrolled so that approximately 70% of randomized subjects will have taken at least 1 prior migraine prevention medication with proven efficacy.

Randomization will be stratified by site and by prior exposure (yes/no) to a migraine prevention medication with proven efficacy.

After finishing the double-blind treatment period, completers in the placebo arm will be re-randomized to atogepant 10 mg, atogepant 30 mg, or atogepant 60 mg arm (dose blinded) in a 1:1:1 ratio in the active treatment extension period.

2.4 Sample Size Determination

A sample size of 130 subjects per treatment group provides approximately 88%, 94% or 99% power to show statistically significant improvement between each of the three atogepant doses (10 mg, 30 mg, or 60 mg) and placebo for the primary efficacy endpoint, respectively, on the mITT analysis set. Assumptions used in the sample size calculation are based on results from the ADVANCE study in a US adult population.¹

The assumed treatment difference between each atogepant dose versus placebo and the standard deviation for the primary endpoint are shown in [Table 1](#). The dropout rate is assumed to be approximately 5.4% for the double-blind treatment period because the observed dropout rate was less than 5% for trials conducted in Japanese patients with EMs.²⁻⁵ All statistical powers presented in this section were calculated adjusting for multiple comparisons using the Hochberg procedure with the family-wise Type I error rate being controlled at a 0.05 level (2-sided).

Table 1. Power and Sample Size Calculations for the Endpoint, Change from Baseline in Monthly Migraine Days Across the 12-Week Treatment Period

Randomized n/arm	Effective n/arm	Treatment Arm	Treatment Difference	Standard Deviation	Power for individual Dose	Probability (At Least one arm is significant)
130	123	60 mg	1.7	3	0.986	0.992
		30 mg	1.38	3	0.937	
		10 mg	1.21	3	0.877	

3.0 Endpoints

3.1 Primary Endpoint

The primary efficacy endpoint is the change from baseline in mean monthly migraine days across the 12-week double-blind treatment period. Baseline is defined as the number of migraine days during the last 28 days prior to the randomization date.

3.2 Secondary Endpoints

The secondary efficacy endpoints are:

- Change from baseline in mean monthly headache days across the 12-week double-blind treatment period.
- Change from baseline in mean monthly acute medication use days across the 12-week double-blind treatment period.
- At least a 50% reduction in the 3-month average of monthly migraine days.
- Change from baseline in MSQ v2.1 Role Function-Restrictive domain score at Week 12.
- Change from baseline in mean monthly Performance of Daily Activities domain score of the AIM D across the 12-week double-blind treatment period.
- Change from baseline in mean monthly Physical Impairment domain score of the AIM-D across the 12-week double-blind treatment period.

3.3 Additional Efficacy Endpoints

Additional efficacy endpoints are:

- $\geq 25\%$, $\geq 50\%$, $\geq 75\%$, 100% improvement (decrease) in monthly migraine days at Weeks 1-4, 5-8, and 9-12.
- $\geq 25\%$, $\geq 75\%$, 100% improvement (decrease) in the 3-month average of monthly migraine days.
- Change from baseline in monthly migraine days at Weeks 1-4, 5-8, and 9-12.
- Change from baseline in monthly headache days at Weeks 1-4, 5-8, and 9-12.
- Change from baseline in monthly cumulative headache hours at Weeks 1-4, 5-8, 9-12, and average across the 12-week double-blind treatment period.
- Change from baseline in monthly acute medication use days at Weeks 1-4, 5-8, and 9-12.
- Change from baseline in monthly triptan use days at Weeks 1-4, 5-8, 9-12, and average across the 12-week double-blind treatment period.
- Change from baseline in monthly moderate/severe headache days at Weeks 1-4, 5-8, 9-12, and average across the 12-week double-blind treatment period.
- Change from baseline in monthly severe headache days at Weeks 1-4, 5-8, 9-12, and average across the 12-week double-blind treatment period.
- Change from baseline in weekly migraine days at Weeks 1-4.
- Having a migraine day on the day of initial dose and on each day of the 6 days post the initial dose.
- Change from baseline in monthly headache days with nausea and /or vomiting symptom across the 12-week double-blind treatment period
- Change from baseline in monthly headache days with photophobia across the 12-week double-blind treatment period
- Change from baseline in monthly headache days with phonophobia across the 12-week double-blind treatment period
- Change from baseline in the HIT-6 total score at Weeks 4, 8, and 12.
- At least a 5-point improvement (decrease) from baseline in HIT-6 total score at Weeks 4, 8, and 12.

- Assessed by the PGIC as "much better" or "very much better" at Week 12.
- "Satisfied" or "extremely satisfied" with study medication for migraine prevention at Weeks 4, 8, and 12.
- Change from baseline in percent work time missed, percent impairment while working, percent overall impairment, and percent activity impairment due to migraine at Weeks 4, 8, and 12 as assessed by the WPAI:MIGRAINE.
- Change from baseline in the MIDAS total score at Week 12.
- Change from baseline in MIDAS absenteeism score (Questions 1, 3, and 5) at Week 12.
- Change from baseline in MIDAS presenteeism score (Questions 2 and 4) at Week 12.
- Change from baseline in PGI-S score at Weeks 4, 8, and 12.
- Change from baseline in the MSQ v2.1 Role Function-Preventive domain score at Weeks 4, 8, and 12.
- Change from baseline in the MSQ v2.1 Role Function-Restrictive domain score at Weeks 4 and 8.
- Change from baseline in the MSQ v2.1 Emotional Function domain score at Weeks 4, 8, and 12.
- Change from baseline in monthly Performance of Daily Activities domain score of the AIM-D at Weeks 1-4, 5-8, and 9-12.
- Change from baseline in monthly Physical Impairment domain score of the AIM-D at Weeks 1-4, 5-8, and 9-12.
- Change from baseline in monthly AIM-D total score at Weeks 1-4, 5-8, 9-12, and average across the 12-week double-blind treatment period.
- Change from baseline in monthly Activity Level at Weeks 1-4, 5-8, 9-12, and average across the 12-week double-blind treatment period.
- Change from baseline in monthly Activity Limitation at Weeks 1-4, 5-8, 9-12, and average across the 12-week double-blind treatment period.
- Change from baseline in PHQ-9 score at Week 12.
- Change from baseline in EQ-5D-5L descriptive system index score at Weeks 1 to 2, and at specified windows around Weeks 4, 8, and 12.

- Change from baseline in the EQ-5D-5L VAS score at Weeks 1 to 2, and at specified windows around Weeks 4, 8, and 12.
- Change from baseline in PROMIS-PI total score at Weeks 4, 8, and 12.

3.4 Safety Endpoints

Safety evaluations include AE monitoring, vital sign measurements, ECG variables, clinical laboratory testing (hematology, chemistry, and urinalysis), and C-SSRS as measures of safety and tolerability for the entire study duration.

4.0 Analysis Populations

The following population sets will be used for the analyses.

The Screened Population consists of all subjects who signed informed consent.

The Intent-to-Treat (ITT) population includes all randomized subjects.

All efficacy analyses will be performed using the modified Intent-to-Treat (mITT) population, consisting of all randomized subjects who received at least 1 dose of study drug, had an evaluable baseline period of eDiary data and had at least 1 evaluable post-baseline 4-week period (Weeks 1 to 4, 5 to 8, and 9 to 12) of eDiary data. Refer to SAP [Appendix B](#) for the definition of evaluable baseline and post-baseline period. For efficacy analyses, subjects will be included in the analysis according to the treatment group to which they were randomized (as randomized).

All safety analyses will be performed using the Safety Populations: Safety population 1 and Safety population 2. Safety Population 1 consists of all subjects who received at least 1 dose of study drug during the double-blind treatment period. Safety Population 2 consists of all subjects who received at least 1 dose of study drug during the active treatment extension period. For safety data analyses, the subjects will be analyzed according to actual treatment received (rather than as randomized). A subject's actual treatment will be determined by the first dose of study treatment.

5.0 Subject Disposition

The total number of subjects who were screened, enrolled (randomized), and treated will be summarized. Reasons for exclusion, including screen failure, will be summarized.

The number of randomized subjects will also be summarized by treatment group for the following factors:

- Randomization stratification factor (prior exposure [yes/no] to a migraine prevention medication with proven efficacy from IWRS;
- Prior exposure to migraine prevention medication with proven efficacy based on prior medication collected eCRF (derived as specified in [Appendix E](#)), which will be termed as "actual strata" in the SAP.

A listing of subjects with incorrect randomization stratum will be provided.

A summary of subject accountability by investigator will be provided where the number of subjects in each of the following categories will be tabulated for each treatment group:

- Subjects randomized in the study;
- Subjects who took at least one dose of study treatment;
- Subjects who completed study treatment;
- Subjects who prematurely discontinued study treatment;
- Subjects in the mITT population;
- Subjects in the Safety Populations 1 and 2.

The summary of subject accountability by investigator also will include the number of subjects who screened and the number of subjects who screen failed.

The number and percentage of subjects in the Safety Populations who prematurely discontinued study treatment will be summarized by reason for not completing study treatment overall and by treatment group.

6.0 Study Treatment Duration and Compliance

For the Safety Populations, duration of treatment will be summarized for each treatment group. The treatment groups for active treatment extension period will also include three additional columns for the lead-in placebo re-randomized group. Duration of treatment is defined for each subject as last dose date minus first dose date + 1. Duration of treatment for a treatment period is defined for each subject as last dose date minus first dose date + 1. Duration of treatment will be summarized separately for each period (double-blind treatment period and active treatment extension period) using the number of subjects treated, mean, standard deviation, median, Q1, Q3, minimum and maximum. In addition, the number and percentage of subjects in each treatment duration interval for double-blind treatment period and active treatment extension period (≥ 1 day, ≥ 7 days, ≥ 14 days, ≥ 21 days, ≥ 28 days, ≥ 35 days, ≥ 42 days, ≥ 49 days, ≥ 56 days, ≥ 63 days, ≥ 70 days, ≥ 77 days, ≥ 84 days) and overall (≥ 1 day, ≥ 7 days, ≥ 14 days, ≥ 21 days, ≥ 28 days, ≥ 35 days, ≥ 42 days, ≥ 49 days, ≥ 56 days, ≥ 63 days, ≥ 70 days, ≥ 77 days, ≥ 84 days, ≥ 91 days, ≥ 98 days, ≥ 105 days, ≥ 112 days, ≥ 119 days, ≥ 126 days, ≥ 133 days, ≥ 140 days, ≥ 147 days, ≥ 154 days, ≥ 161 days, ≥ 168 days) will be summarized by treatment group.

Subject-years, defined as exposure to the study treatment in years, will be summarized by treatment group for the Safety Populations.

Treatment compliance for a specified period is defined as the total number of study medications actually taken by a subject during that period divided by the number of study medications that were expected to be taken during the same period multiplied by 100. The total number of actual capsules taken during a specific period will be calculated from the study medication record.

Descriptive statistics for study medication dosing compliance together with the compliance categories ($< 80\%$, $80\% - 120\%$, $> 120\%$) will be summarized by study treatment group for each period between 2 consecutive visits, for the period from the first dose of the double-blind study interventions actually taken to the last dose of double-blind

study intervention actually taken, as well as for the period from the first dose of the active treatment extension period interventions actually taken to the last dose of the active treatment extension period intervention actually taken for the Safety Populations 1 and 2, respectively.

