10.0 Safety Analyses

10.1 General Considerations

For the purposes of safety analysis, the start of the active treatment extension period is marked by the date of the first dose of study medication received in the active treatment extension period (Visit 6, Visit 7, or Visit 8).

Safety data will be summarized for the Safety Populations 1 and 2. Safety summaries will be presented by treatment groups. For the safety analysis, subjects are assigned to a treatment group based on the treatment actually received, regardless of the treatment randomized.

The safety parameters will include AEs, clinical laboratory evaluations, vital sign measurements, ECG parameters, and the C-SSRS. For each of the clinical laboratory, vital sign, and ECG parameters, the last non-missing safety assessment before the first dose of treatment will be used as the baseline for all analyses of that safety parameter.

Continuous variables will be summarized by the number of subjects, and mean, SD, median, Q1, Q3, minimum, and maximum values. Categorical variables will be summarized by number and percentage of subjects.

Descriptive statistics for safety endpoints will be provided by treatment period (double-blind treatment period or active treatment extension period), separately. For selected safety endpoints, analyses will be provided across both treatment periods to show the trend over time.

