10.2.3 Treatment-Emergent Adverse Events by SOC and/or PT

Treatment-emergent adverse events will be summarized by treatment group, for each treatment period and overall, by SOC and PT; by maximum relationship to study treatment as assessed by the investigator (e.g., reasonable possibility or no reasonable possibility) and SOC and PT; by maximum severity and SOC and PT; and by subject number and SOC and PT. Specific adverse events will be counted once for each subject for calculating percentages, unless stated otherwise. In addition, if the same adverse event occurs multiple times within a subject, the highest severity and level of relationship to investigational product will be reported.

The incidence of common ($\geq 2\%$ of subjects in any treatment group) TEAEs will be summarized by preferred term, and treatment group. A similar 5% table will be provided as well.

10.2.4 Deaths, Serious Adverse Events, and Adverse Events Leading to Study Treatment Discontinuation

Treatment-emergent serious adverse events (TESAEs) and TEAEs leading to premature discontinuation of study treatment will be summarized by SOC and PT for each treatment period. TESAEs will also be summarized by SOC and PT overall.

For TEAEs leading to premature discontinuation of study treatment, summaries by SOC and PT will be provided as follows:

- TEAEs with start date and treatment discontinuation date in the double-blind period
- TEAEs with start date and treatment discontinuation date in the extension period
- TEAEs leading to treatment discontinuation during the extension period, i.e., the treatment discontinuation date occurred in the extension period regardless of whether the TEAE started in the double-blind period or the extension period.

Tabular listings will be provided for all deaths, all SAEs and TEAEs leading to premature discontinuation of study treatment.

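### The SAP defines extension columns for re-randomized placebo subjects only for treatment duration; for adverse events and discontinuations the grouping is open, and both literal readings give rates that are hard to interpret

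*SAP*

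**What the plan says.** Protocol 4.1 and SAP 2.2 describe two routes into the 12-week extension. Subjects who complete the double-blind period on atogepant stay on their dose. Placebo completers are re-randomized 1:1:1 to 10, 30 or 60 mg. Everyone treated in the extension is therefore on one of three doses, by one of two routes.

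The SAP names the second route as a separate display group once, in the duration-of-treatment text of section 6.0: "The treatment groups for active treatment extension period will also include three additional columns for the lead-in placebo re-randomized group". Elsewhere:

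- SAP 5.0: subjects in the Safety Populations who "prematurely discontinued study treatment will be summarized by reason for not completing study treatment overall and by treatment group".
- SAP 10.1: "For the safety analysis, subjects are assigned to a treatment group based on the treatment actually received, regardless of the treatment randomized".
- SAP 10.2.3: "Treatment-emergent adverse events will be summarized by treatment group, for each treatment period and overall, by SOC and PT".
- SAP 10.2.4 adds a summary of "TEAEs leading to treatment discontinuation during the extension period, i.e., the treatment discontinuation date occurred in the extension period", wherever the event began. It names no lead-in split.
- SAP 4.0, directly after defining both Safety Populations: "A subject's actual treatment will be determined by the first dose of study treatment". No period is named.

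Protocol 7.5 and SAP 10.1 also plan analyses across both periods, for selected safety endpoints, to show change over time.

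**The concern.** The two routes bring different subjects into the extension. A continuing subject has, by design, completed 12 weeks on the same dose. A lead-in placebo subject is taking atogepant for the first time. The protocol's own withdrawal rules sharpen the difference. Section 5.5 requires withdrawal after a serious hypersensitivity event, after a nonserious one unless there is a clear alternative cause, and for liver-test cases not rechallenged. For those harms the continuing subjects have already been filtered and the new starters have not. Hypersensitivity is the newly identified risk in Protocol 2.2, and liver events are under close surveillance there.

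If the routes share a column, the extension rate is neither a first-exposure rate nor a weeks 13 to 24 rate, and a change between periods mixes time on drug with an influx of new starters. If re-randomized subjects instead stay labelled as placebo, events that begin on atogepant are reported under placebo. In both cases exposure is shown by route under SAP 6.0 but harms cannot be matched to it. The study is intended to support registration in Japan, so these tables will be read closely.

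**Working it through.** **Inputs.** From Protocol 7.8 and SAP 2.4: 130 randomized per arm, 5.4% dropout in the double-blind period, 123 effective per arm. From Protocol 4.1: 1:1:1 re-randomization of placebo completers. The documents give no adverse event rates, so all rates below are assumptions.

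**Plan's own figures.** 130 × (1 − 0.054) = 122.98, that is 123, as stated. A simulation of one million trials under the Hochberg procedure, with the stated differences and SD of 3, gives power of 0.877, 0.938 and 0.987 for 10, 30 and 60 mg, and 0.993 for at least one dose. The plan states 0.877, 0.937, 0.986 and 0.992. Nothing in this point touches those figures.

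**Size of the mix.** Take 123 as the number per arm entering the extension.

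- New starters per dose: 123 / 3 = 41.
- Pooled dose column: 123 + 41 = 164.
- Share of new starters: 41 / 164 = 25%.

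With no dropout: 130 / 3 = 43.3, and 43.3 / 173.3 = 25%. The share does not depend on dropout as long as the same proportion of each arm enters the extension.

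**Reading 1: group by treatment actually received (SAP 10.1).** Let a be the 12-week rate in first-time users and b the rate in continuing users.

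Pooled rate = 0.25a + 0.75b, so pooled / a = 0.25 + 0.75(b / a).

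| a (assumed) | b (assumed) | Pooled | Pooled / a |
|---|---|---|---|
| 10% | 0% | 2.5% | 25% |
| 10% | 2% | 4.0% | 40% |
| 10% | 5% | 6.25% | 62.5% |
| 10% | 10% | 10% | 100% |
| 5% | 0% | 1.25% | 25% |
| 5% | 1% | 2.0% | 40% |
| 5% | 2% | 2.75% | 55% |
| 5% | 5% | 5% | 100% |

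If b does not exceed a, the pooled rate lies between 25% and 100% of the first-exposure rate. There is no dilution when b = a.

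For a rare event with none observed, the one-sided 95% upper bound is 1 − 0.05^(1/n). That is 1.8% for a pooled 164, 7.0% for the 41 new starters alone, and 2.3% for 130 in the double-blind period. The pooled column would suggest more reassurance about first exposure in the extension than its new starters can give.

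**Reading 2: actual treatment fixed by the first dose (SAP 4.0).** A lead-in placebo subject's first dose of study treatment was placebo. Taken literally, about 3 × 41 = 123 subjects, all on atogepant and split over three doses, would be labelled placebo in the extension and in the overall tables of SAP 10.2.3. This conflicts with SAP 10.1 and with the dose-wise columns of SAP 6.0.

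**Reading 3: SAP 6.0 defines the extension groups everywhere.** This gives six columns and solves the problem. But the sentence stands inside the duration text, and it does not say whether the three dose columns beside the additional ones hold continuing subjects only.

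**Overall tables.** A re-randomized subject actually received both placebo and a dose of atogepant, so SAP 10.1 does not settle the overall column either. In the last summary of SAP 10.2.4, an event that began on placebo but led to stopping in the extension would, under Reading 1, be counted against an atogepant dose.

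**The case against.** The strongest reply is that pooling is nowhere stated. The phrase on treatment actually received is the usual contrast with treatment as randomized, there to handle dosing errors, and says nothing about combining treatment sequences. The grammatical subject of the SAP 6.0 sentence is the extension treatment groups, so it can fairly be read as defining them once, with later sections inheriting the definition. This stands: a reader who concludes that the SAP plans pooled tables goes beyond the text. The supportable statement is that the columns are undefined for these tables.

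A reader might also infer that pooling would hide first-exposure harm, or that the trial loses its only randomized dose comparison in new starters. The documents support neither. Safety Population 1 with the period-specific event rules gives first-12-week rates from about 130 subjects per dose, roughly three times the 41 in the extension, with concurrent placebo. The 1:1:1:1 randomization compares doses in first-time users there. The re-randomized comparison stays recoverable from subject-level data; it would simply not be tabulated. What pooling would obscure is the further 41 first exposures per dose (41 / 130 = 32% more) and the meaning of the extension tables.

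Finally, safety analyses are descriptive, the layout of the trend displays is unspecified, and more columns mean sparser tables. That is a reason to keep the change modest. It does not justify leaving three incompatible readings open.

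**Conclusion.** The point holds as a gap in definition. Only SAP 6.0 names the lead-in placebo columns, and only for duration. SAP 10.1 and the first-dose rule in SAP 4.0, each taken literally, lead to different tables, and neither gives an interpretable extension rate.

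On planning figures, pooling would make new starters 25% of each dose column (41 of 164). This assumes that equal proportions of each arm enter the extension. The pooled rate would then be 25% to 100% of the first-exposure rate, assuming continuing subjects do not have the higher rate. Any single percentage for the understatement would rest on event rates the documents do not give.

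The consequence is confined to the extension tables, the overall tables and the displays across periods. First-exposure harm remains estimable from the double-blind period, and efficacy, type I error and power are untouched. This is an inexpensive improvement to the plan, not a threat to the trial's conclusions.

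**What to change.** - **SAP 5.0 and 10.1:** state that Safety Population 2 tables of discontinuation by reason, TEAEs, SAEs and TEAEs leading to discontinuation, and the key laboratory summaries, use six columns: continuing 10, 30 and 60 mg, and placebo to 10, 30 and 60 mg. Show pooled dose columns only alongside these.
- **SAP 6.0:** say that the three dose columns beside the additional ones hold continuing subjects only, so that exposure and harms match.
- **SAP 10.1:** base displays of trend over time on continuing subjects.
- **SAP 4.0:** state that actual treatment is set by the first dose within each period.
- **SAP 10.2.3:** state how re-randomized subjects enter the overall tables.

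The cost is a few sentences and wider table shells. No new data are needed, and the sponsor already plans the lead-in columns for exposure. The downside is imprecision in columns of about 41 subjects, where one event is 1 / 41 = 2.4%.
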